**COMPARISON OF THE VALIDITY AND RELIABILITY OF THREE
DIFFERENT METHODS USED FOR WRIST PROPRIOCEPTION
MEASUREMENT**

The most recently revised date: 06.25.2018

**The Human Subjects Protection Review Board
approbation date: 06.25.2018**

STUDY PROTOCOL

Participants

The prior sample size calculation section of G*Power 3.1.9.2 software revealed that the inclusion of 32 healthy participants (64 wrists) was necessary for achieving 95% power. Individuals who suffered an injury or underwent a surgical procedure in the last six months that could affect hand functions or senses were excluded from the study. Additionally, individuals with a history of neuromuscular disease, traumatic nerve injury, congenital anomalies, or skin infections were excluded. An informed consent form was obtained from all participants. An independent ethics committee approved the study (approval number:24074710--028).

Instrumentation

The Cybex isokinetic dynamometer [Cybex NORM®, Humac, CA, USA] was used as a reference standard to test the validity of the universal goniometer, inclinometer [Acumar, Lafayette Instrument Co., Lafayette, USA], and JPSG. The isokinetic dynamometer is a well-known instrument for measuring passive and active joint position sense (AJPS) and provides a target angle result without rater bias (Relph & Herrington, 2015). The Cybex isokinetic dynamometer has a good reliability in evaluating wrist AJPS (Seven et al., 2019).

Procedures

The evaluation of proprioception using the isokinetic dynamometer was performed with the participants in sitting. The shoulder was positioned in the midline, the elbow was flexed about 90°, and the wrist was positioned in supination (Brown, 2000). During the evaluation, the forearm was fixed with a strap to prevent the forearm from moving and changing the angle of the wrist. The rotation axis of the dynamometer was aligned with the diagonal axis of the distal tubercle of radius and the head of ulna (Figure 1). The

wrist was placed in a 0° position. In this starting position, the range of motion was set as 40° flexion and 40° extension (Ellenbecker et al., 2006). The device was calibrated before the evaluation of each participant.

The goniometric (1° scale increments) measurement was performed with the elbow positioned at 90° flexion and resting on the table, the forearm was in mid-pronation, and the fingers were relaxed (Hagert, 2010; Karagiannopoulos et al., 2016; Pilbeam & Hood-Moore, 2018). The movement axis of the mid-carpal and radiocarpal joints is defined as the pivot point of the goniometer to ensure a compatible measurement of wrist movement. The stable arm of the goniometer was placed parallel to the radius, and the mobile arm was followed the third metacarpal bone (Figure 2) (Pilbeam & Hood-Moore, 2018).

The JPSG consists of two wooden boards fixed at an angle of 90° . The plate perpendicular to the ground has an opening that the wrist can go through. 0 to 180° angle values with 1° increment were drawn on the plate that parallels the floor (Erdem, 2013). For the evaluation, the participant was asked to sit in front of the table with the trunk upright and the shoulder in the neutral position. The patient's forearm passed through the opening in the JPSG, and the wrist joint was adjusted to match the axis of movement (Figure 3). The forearm was positioned in mid-pronation, the wrist was positioned at 0° flexion/extension, and the forearm was in the neutral position. Participants were asked not to contact the plates during the measurements.

Another tool used to evaluate wrist AJPS was the digital dual inclinometer. The limb position used during the inclinometer evaluations was the same as the position for the goniometer. One of the inclinometer sensors was placed on the 3rd metacarpal bone on the dorsal side of the hand. The other sensor was placed on the dorsal side of the forearm, perpendicular to the flexion/extension movement axis (Figure 4).

AJPS was measured to evaluate wrist proprioception. An eyepatch was used during all tests to prevent visual stimuli, and the evaluations were performed in a quiet room. The

30° extension, which is the functional position of the wrist, was selected as the target angle for AJPS assessment (Neumann, 2002; Seven et al., 2019). After the test was explained to the participants, they were asked to actively bring the wrist from the neutral (0° flexion/extension) to 30° extension (a barrier was placed at 30° line) and wait for 5 seconds at this position. The participants were then asked to return to the starting position (a block was also placed at 0°). The participants were then asked to find the target angle. This trial was repeated three times. The amount of error between the target and achieved angles were recorded as the absolute angular error. The relative error amount was calculated using the arithmetic mean of these three absolute angular errors (Suner-Keklik et al., 2017). The same measurements were repeated for the other limb. The same rater performed all measurements.

All evaluations were repeated at the same hour of the day, seven days after the first measurement by the same rater to examine the test-retest reliability of the methods (Holmbäck et al., 1999). To avoid the learning effect (Feiring et al., 1990), the order which extremities were assessed (right/left) was determined using a web-based “Random Sequence Generator Application” (<https://www.random.org/sequences/>). The same randomization method was used to determine the order of the evaluation methods. The sequence used for each participant on the first evaluation was repeated on the second evaluation. A five-minute rest period was given between each measurement to eliminate the effect of muscle fatigue. As AJPS was demonstrated to significantly reduce during the menstruation period, the evaluation days of the female participants were arranged not to coincide with the week of menstruation (Aydoğ et al., 2005).

REFERENCES

- Brown LE 2000 Isokinetics in human performance. *Human Kinetics*.

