**COMPARISON OF THE VALIDITY AND RELIABILITY OF THREE
DIFFERENT METHODS USED FOR WRIST PROPRIOCEPTION
MEASUREMENT**

The most recently revised date: 06.25.2018

**The Human Subjects Protection Review Board
approbation date: 06.25.2018**

Statistical Analysis

Statistical analysis was performed using the SPSS version 28 (IBM, Armonk, NY) computer software system. The Normality of the variables was tested using the Shapiro-Wilk test. Since the data were non-parametric, the validity analysis was performed using Spearman's correlation test. The validity of these three methods was calculated according to their correlation with the isokinetic dynamometer data. Correlation coefficients was used to interpret the results. The correlation coefficient was defined as follows: between 0.90-1.00 was very high, between 0.70-0.90 was high, between 0.50-0.70 was medium, between 0.30-0.50 was weak, and less than 0.30 was negligible (Mukaka, 2012). The statistical significance level was determined as $p < 0.05$ for all analyses.

The Intraclass Correlation Coefficients $ICC_{3,1}$ (two-way mixed, absolute agreement) were calculated for test-retest reliability analysis. The $ICC_{2,1}$ value that was greater than 0.90 was defined as an excellent correlation, a good correlation between 0.75 and 0.90, a moderate correlation between 0.50-0.75 and a poor correlation if less than 0.50 (Koo & Li, 2016). Measurement errors of the three methods were used to calculate standard error of measurement (SEM) and Minimal Detectable Change (MDC) in a 95% confidence interval (Haley & Fragala-Pinkham, 2006; Suner-Keklik et al., 2017).

RESULTS

A total of 32 participants (64 wrists) were evaluated in the study (Figure 5). Demographic characteristics are presented in Table 1.

[figure not shown]

Table 1. Demographic features

	Minimum	Maximum	Mean ± S.D.
Age	19.00	31.00	23.34 ± 3.84
Height	160.00	193.00	173.66 ± 8.87
Weight	48.00	115.00	68.31 ± 13.75
BMI	17.56	33.97	22.52 ± 3.29

BMI: Body Mass Index

The results of the validity analysis of the methods are displayed in Table 2. The validity of these methods was found to be weak for the inclinometer and JPSG and moderately for the goniometer (Mukaka, 2012) (Table 2).

Table 2. The results of validity analysis and descriptive statistics of the methods

Methods	Median (25th per – 75th per)	r	P
Isokinetic dynamometer	3.17° (2.33° – 4.83°)	-	-
Inclinometer	3.66° (2.66° – 5.83°)	0.350	0.005*
Goniometer	3.50° (2.33° – 4.66°)	0.529	<0.001*

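### Each method and the dynamometer are scored on separate reproductions in different forearm positions, so the banded r in Table 2 does not support a conclusion about the instruments

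*Protocol*

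**What the plan says.** Protocol, Instrumentation, makes the isokinetic dynamometer the reference for the other three tools. Protocol, Procedures, sets the postures: supination with a strapped forearm on the dynamometer, and mid-pronation for the goniometer, the inclinometer (same limb position as the goniometer) and the JPSG.

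The test itself is described once for all methods: "The participants were then asked to find the target angle. This trial was repeated three times". The score is the mean of the three absolute errors. The order of methods is randomised, and "A five-minute rest period was given between each measurement to eliminate the effect of muscle fatigue". All evaluations are repeated a week later.

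SAP, Statistical Analysis, states: "The validity of these three methods was calculated according to their correlation with the isokinetic dynamometer data". It grades the coefficient on fixed bands, including "between 0.50-0.70 was medium, between 0.30-0.50 was weak". SAP, Results, then calls validity weak for the inclinometer (0.350) and JPSG (0.432) and moderate for the goniometer (0.529). Table 3 gives test-retest ICCs for these three methods and none for the dynamometer.

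**The concern.** If an instrument and its reference read the same movement, the only thing that can pull their scores apart is the instruments. Here they score different movements. A participant who repositions well in one set of three attempts and less well in the next lowers r just as an inaccurate goniometer would. So does any real difference in position sense between supination and mid-pronation.

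Validity is in the study title and is the first result reported. If accurate instruments could earn the same labels, then calling a method weak or moderate says little about the tool, and a reader choosing between the tools may be misled.

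**Working it through.** **1. Are the performances separate?** The sentence on rest periods does not settle this alone, because *measurement* could mean a limb or a method. Three other facts do:
- The dynamometer posture and the posture for the other methods cannot be held in one movement.
- The order of methods is randomised.
- SAP Table 4 puts the three methods in first, second and third place, with every row and column summing to 64.

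The dynamometer is not in Table 4, so its place in the sequence is not stated.

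**2. Reproducing Table 2.** Inputs are the three r values and "A total of 32 participants (64 wrists) were evaluated in the study". With t = r·√[(n − 2)/(1 − r²)], two-sided, n = 64:
- 0.350: t = 0.350·√(62/0.8775) = 2.94, p = 0.0046 (stated 0.005)
- 0.432: t = 0.432·√(62/0.8134) = 3.77, p = 0.0004 (stated <0.001)
- 0.529: t = 0.529·√(62/0.7202) = 4.91, p = 0.000007 (stated <0.001)

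All three agree. With n = 32, r = 0.350 would give p = 0.0496, so wrists were the units.

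**3. What r would error-free devices give?** Signed error on attempt j of wrist i is b_i + w_ij, with b_i ~ N(0, ρσ²) stable for the wrist and w_ij ~ N(0, (1 − ρ)σ²) new at each attempt. The score is the mean of three absolute errors. Two devices with zero measurement error each score their own three attempts. σ is set so that the median is the dynamometer's 3.17°; the reported quartiles are 2.33° and 4.83°. **ρ is an assumption, because the documents do not report it.** Each row uses 200,000 simulated wrists.

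| ρ | Simulated quartiles | Spearman r |
|---|---|---|
| 0.3 | 2.23°, 4.29° | 0.15 |
| 0.4 | 2.21°, 4.36° | 0.24 |
| 0.5 | 2.18°, 4.47° | 0.35 |
| 0.6 | 2.15°, 4.62° | 0.47 |
| 0.7 | 2.09°, 4.84° | 0.59 |
| 0.8 | 1.97°, 5.13° | 0.72 |

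Values of ρ from 0.5 to 0.7 cover all three reported coefficients. Two variants point the same way:
- If wrists differ in spread instead of bias (log-normal SD with log-SD 0.3, 0.4, 0.5), r is 0.28, 0.41 and 0.51.
- If part of the variance shifts from set to set (shares 0.6 stable, 0.1 set, 0.3 trial), r falls to 0.40.

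In samples of 64, r lies between 0.30 and 0.70 in 65%, 93% and 90% of runs at ρ = 0.5, 0.6 and 0.7.

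**4. Comparison: both devices read the same movement.** Error-free devices give r = 1.00 by construction, and about 0.99 with rounding to 1°. A device error SD of 4° per attempt gives r of 0.47 to 0.56, and 5° gives 0.36 to 0.46 (ρ from 0.3 to 0.7). An r of 0.35 to 0.53 would then point to a device error of roughly 4° or more. Under the actual design it need not point to any.

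**5. A rough ceiling from Table 3.** Two scores cannot be expected to correlate above √(reliability₁ × reliability₂). Even with dynamometer reliability set to 1, the ceilings are √0.422 = 0.65 (goniometer), √0.369 = 0.61 (JPSG) and √0.114 = 0.34 (inclinometer), all below the 0.70 that starts the high band. With an assumed 0.75 to 0.90 they are 0.56–0.62, 0.53–0.58 and 0.29–0.32. These are indicative only: the ICCs mix participant and device variation over a week, and the inclinometer's 0.350 already exceeds its ceiling.

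**The case against.** **The study validates whole test procedures, not angle readings.** The title speaks of methods, and the score is a repositioning error. For that purpose separate administrations are a legitimate design, because set-to-set variation is part of what a user receives. This stands as a reading of r, and it is the reading the fix adopts. It does not rescue the labels, because Protocol, Instrumentation, frames the aim as the validity of the instruments.

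**The simulation shows possibility only.** This stands. The assumed split drives the answer, and no row of the table matches both reported quartiles. A stable share of 0.8 or more would put r above 0.70, higher than any reported value.

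**A reader might infer that participant variation and device error cannot be separated at all.** The documents do not support that. The protocol repeats all evaluations after a week and does not except the dynamometer. If its reading error is small, its own retest correlation estimates what an accurate device would give in that posture. The three attempts per session also inform the variance split. What is missing is an analysis.

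**A reader might infer that the devices are accurate after all.** That does not follow either. Medians differ (JPSG 2.50° against 3.17°) and the inclinometer's retest ICC is 0.114, so device or posture effects may well be present.

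**The bias is toward low r, so no device is wrongly endorsed.** This is true, and Table 3 already shows poor repeatability. It reduces the urgency but leaves the unsupported conclusion in place.

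**Conclusion.** The point holds as a limit on interpretation, and it should be fixed. Each r in Table 2 reflects three things together: device error, the participant's variation between sets of attempts, and the change from supination to mid-pronation. Under plausible but assumed variance splits, error-free devices would give r of about 0.2 to 0.7, a range that contains 0.350, 0.432 and 0.529. The weak and moderate labels therefore do not support a conclusion about the instruments.

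This rests on separate performances, which the incompatible postures and the randomised order establish, and on a wrist-to-trial variance split that the documents do not give. It does not show that the instruments are accurate, and it does not make the data unusable.

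**What to change.** **(a) Add the dynamometer's own retest result.** Report its seven-day coefficient beside Table 3, as both Spearman r and ICC, with confidence intervals, and interpret each method's r against it as an approximate ceiling. Note two limits. A seven-day gap is not the same as a comparison within one session, and 64 wrists give an imprecise estimate: at ρ = 0.6 the simulated 95% range of r is 0.23 to 0.65. Also state which session Table 2 uses, because its inclinometer median (3.66°) matches neither session in Table 3 (5.33° and 4.50°).

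**(b) Restate the conclusion in SAP, Results.** For example: *Scores on the inclinometer, goniometer and JPSG tests correlated 0.350, 0.529 and 0.432 with scores on a separately performed dynamometer test in a different forearm position. These coefficients describe association between tests and are not graded as instrument validity.*

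**Cost.** A little more analysis, no new testing if the repeat dynamometer data were kept, and a less favourable validity statement.

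Paired readings of two instruments on the same movement are a suggestion for a future study only. They would change the posture of the tests being validated, and results for all 32 participants are already reported.

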**COMPARISON OF THE VALIDITY AND RELIABILITY OF THREE
DIFFERENT METHODS USED FOR WRIST PROPRIOCEPTION
MEASUREMENT**

The most recently revised date: 06.25.2018

**The Human Subjects Protection Review Board
approbation date: 06.25.2018**

Statistical Analysis

Statistical analysis was performed using the SPSS version 28 (IBM, Armonk, NY) computer software system. The Normality of the variables was tested using the Shapiro-Wilk test. Since the data were non-parametric, the validity analysis was performed using Spearman's correlation test. The validity of these three methods was calculated according to their correlation with the isokinetic dynamometer data. Correlation coefficients was used to interpret the results. The correlation coefficient was defined as follows: between 0.90-1.00 was very high, between 0.70-0.90 was high, between 0.50-0.70 was medium, between 0.30-0.50 was weak, and less than 0.30 was negligible (Mukaka, 2012). The statistical significance level was determined as $p < 0.05$ for all analyses.

The Intraclass Correlation Coefficients $ICC_{3,1}$ (two-way mixed, absolute agreement) were calculated for test-retest reliability analysis. The $ICC_{2,1}$ value that was greater than 0.90 was defined as an excellent correlation, a good correlation between 0.75 and 0.90, a moderate correlation between 0.50-0.75 and a poor correlation if less than 0.50 (Koo & Li, 2016). Measurement errors of the three methods were used to calculate standard error of measurement (SEM) and Minimal Detectable Change (MDC) in a 95% confidence interval (Haley & Fragala-Pinkham, 2006; Suner-Keklik et al., 2017).

RESULTS

A total of 32 participants (64 wrists) were evaluated in the study (Figure 5). Demographic characteristics are presented in Table 1.

[figure not shown]

Table 1. Demographic features

	Minimum	Maximum	Mean ± S.D.
Age	19.00	31.00	23.34 ± 3.84
Height	160.00	193.00	173.66 ± 8.87
Weight	48.00	115.00	68.31 ± 13.75
BMI	17.56	33.97	22.52 ± 3.29

BMI: Body Mass Index

The results of the validity analysis of the methods are displayed in Table 2. The validity of these methods was found to be weak for the inclinometer and JPSG and moderately for the goniometer (Mukaka, 2012) (Table 2).

Table 2. The results of validity analysis and descriptive statistics of the methods

Methods	Median (25th per – 75th per)	r	P
Isokinetic dynamometer	3.17° (2.33° – 4.83°)	-	-
Inclinometer	3.66° (2.66° – 5.83°)	0.350	0.005*
Goniometer	3.50° (2.33° – 4.66°)	0.529	<0.001*
JPSG	2.50° (1.66° – 3.33°)	0.432	<0.001*

per: percentile, r: correlation coefficient, °: degree, *: p<0.05

The results of the test-retest reliability analysis of the methods are displayed in table 3. The inclinometer was not found to be a reliable method for evaluating AJPS while the goniometer and JPSG were detected to have significant test-retest reliability. However, the 95% confidence intervals of the goniometer and JPSG were poor (Koo & Li, 2016) (Table 3).

Table 3. The results of test-retest reliability analysis and descriptive statistics

Methods	1st Measurement	2nd Measurement	ICC_{3,1}	P	SE M	MDC
	Median	Median				
	(25 per – 75 per)	(25 per – 75 per)				
Inclinometer	5.33° (3.33° – 8.17°)	4.50° (2.83° – 6.33°)	0.114	0.183	0.11	0.25
Goniometer	3.50° (2.33° – 5.66°)	3.66° (2.33° – 4.83°)	0.422	<0.001*	0.32	0.75
JPSG	2.33° (1.33° – 3.33°)	2.00° (1.33° – 3.33°)	0.369	0.001*	0.29	0.68

(per: percentile, r: correlation coefficient, °: degree, *: p<0.05)

The order in which each method was evaluated is presented in Table 4.

Table 4. The sequences of methods

Methods	First	Second	Third
Goniometer	23 (% 35.9)	24 (% 37.5)	17 (% 26.6)
Inclinometer	19 (% 29.7)	20 (% 31.2)	25 (% 39.1)
JPSG	22 (% 34.4)	20 (% 31.2)	22 (% 34.4)

REFERENCES

- Haley SM, Fragala-Pinkham MA 2006 Interpreting change scores of tests and measures used in physical therapy. *Physical therapy* 86, 735-743.
- Koo TK, Li MY 2016 A guideline of selecting and reporting intraclass correlation coefficients for reliability research. *Journal of chiropractic medicine* 15, 155-163.
- Mukaka MM 2012 A guide to appropriate use of correlation coefficient in medical research. *Malawi Medical Journal* 24, 69-71.

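### The Spearman and ICC p-values treat 64 wrists from 32 people as independent, so they are too small if a person's two wrists are alike

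*SAP*

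**What the plan says.** The Protocol (Participants) sets the sample in both units: "inclusion of 32 healthy participants (64 wrists) was necessary for achieving 95% power". Under Procedures, each person is tested on both sides by one rater: "The same measurements were repeated for the other limb. The same rater performed all measurements". The SAP (Results) confirms the numbers analysed: "A total of 32 participants (64 wrists) were evaluated in the study".

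For validity, the SAP (Statistical Analysis) says that "the validity analysis was performed using Spearman's correlation test", each method being correlated with the isokinetic dynamometer. For reliability it names a single-measure ICC, described as "two-way mixed, absolute agreement) were calculated for test-retest reliability analysis". The threshold is 0.05 throughout. Neither document mentions a participant term, averaging of the two wrists, use of one wrist per person, or any other adjustment for pairing.

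The Results then state that "the goniometer and JPSG were detected to have significant test-retest reliability", and also that "the 95% confidence intervals of the goniometer and JPSG were poor". The limits of those intervals are not printed.

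**The concern.** Two wrists of one person, tested by one rater in one visit, may well give similar errors. The standard p-value for a Spearman correlation or an ICC assumes that every unit is an independent draw. If wrists are the units and the two sides are alike, each person is partly counted twice. The test then rejects too often, and an interval computed the same way is too narrow.

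The p-values carry the claim of significant reliability for the goniometer and the JPSG, and the intervals carry the caution attached to it. A reader choosing between devices relies on both. The estimates of r and ICC, and the strength labels read from them, are not in question.

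**Working it through.** **Inputs.** Table 2 gives r = 0.350 (inclinometer), 0.432 (JPSG) and 0.529 (goniometer), with p = 0.005, <0.001 and <0.001. Table 3 gives ICC = 0.114, 0.369 and 0.422 in the same order, with p = 0.183, 0.001 and <0.001. There are 32 people with 2 wrists each. The left-right correlation ρ is not reported; it is assumed to be 0.3, 0.5 or 0.7.

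**Step 1: which n lies behind the printed p-values?**

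For r: t = r·√[(n−2)/(1−r²)] on n−2 df, two-sided. For the inclinometer at n = 64, t = 0.350·√(62/0.8775) = 2.94, p = 0.0046. At n = 32, t = 0.350·√(30/0.8775) = 2.05, p = 0.0496.

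For the ICC with two sessions: F = (1+ICC)/(1−ICC) on (n−1, n−1) df, upper tail. This assumes no shift between days. For the inclinometer, F = 1.114/0.886 = 1.257; p = 0.183 with 63, 63 df and 0.264 with 31, 31 df.

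| Statistic | Printed p | n = 64 | n = 32 |
|---|---|---|---|
| r inclinometer 0.350 | 0.005 | 0.0046 | 0.0496 |
| r JPSG 0.432 | <0.001 | 0.0004 | 0.0135 |
| r goniometer 0.529 | <0.001 | 0.00001 | 0.0019 |
| ICC inclinometer 0.114 | 0.183 | 0.183 | 0.264 |
| ICC JPSG 0.369 | 0.001 | 0.0012 | 0.0173 |
| ICC goniometer 0.422 | <0.001 | 0.0002 | 0.0072 |

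All six fit 64 and none fits 32. The no-shift assumption affects only the ICC rows. Table 4 counts the same way: its rows (23+24+17, 19+20+25, 22+20+22) and its columns (23+19+22, 24+20+20, 17+25+22) all total 64.

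**Step 2: direction and size.** With no true association, the two wrists of one person add a covariance of ρx·ρy to the sum of cross-products. The variance of r is therefore multiplied by about 1 + ρx·ρy, where x is the method and y the dynamometer. With equal ρ, the effective n is 64/(1+ρ²): 64/1.09 = 58.7, 64/1.25 = 51.2 and 64/1.49 = 43.0. The same factor applies to the ICC test if ρ is the similarity of the two wrists within each session.

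| p at ρ = | 0.3 | 0.5 | 0.7 |
|---|---|---|---|
| r inclinometer | 0.007 | 0.012 | 0.021 |
| r JPSG | 0.0007 | 0.0015 | 0.004 |
| r goniometer | 0.00002 | 0.00006 | 0.0003 |
| ICC inclinometer | 0.19 | 0.21 | 0.23 |
| ICC JPSG | 0.002 | 0.003 | 0.007 |
| ICC goniometer | 0.0004 | 0.0009 | 0.002 |

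Simulation (20,000 data sets of 32 people × 2 wrists) gives the true rejection rate of the nominal 5% test at ρ = 0.3, 0.5, 0.7: plain Spearman 5.7%, 7.7%, 10.8%; plain ICC test 5.5%, 7.0%, 8.6%. With ρ = 0 both stay near 5%, so the excess comes from the pairing.

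**Step 3: intervals.** In simulation with normal data, plain 95% intervals cover about 94%, 92% and 89-90% for r, and 94-95%, 92% and 89-91% for the ICC, at the same three values of ρ. The widest change is the limit in which the second wrist adds nothing (Fisher z for r; the F above for the ICC):

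| 95% interval | n = 64 | n = 32 |
|---|---|---|
| r inclinometer | 0.11 to 0.55 | 0.001 to 0.62 |
| ICC inclinometer | −0.13 to 0.35 | −0.24 to 0.44 |
| ICC JPSG | 0.14 to 0.56 | 0.03 to 0.63 |
| ICC goniometer | 0.20 to 0.60 | 0.09 to 0.67 |

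**The case against.** The strongest reply grants the unit of analysis and disputes the size.

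Table 3 shows how well a wrist agrees with itself a week later. A stable personal trait cannot explain a larger share of the variance than that, so the stable part of left-right similarity is capped near 0.114, 0.369 and 0.422. With each method's ρ set to its ICC and the dynamometer's ρ at its maximum of 1, the effective n is 64/1.114 = 57, 64/1.369 = 47 and 64/1.422 = 45, and p for r is 0.007 (inclinometer), 0.0025 (JPSG) and 0.0002 (goniometer). The borderline 0.0496 needs complete redundancy on a device whose own ICC is 0.114. This argument makes the upper end of the range less likely, but it does not bound similarity shared by both wrists within one visit (placement, attention, rater). The ICCs are also estimates. The n = 32 figures are limits, not predictions.

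A stable personal trait makes the true ICC positive, so it cannot inflate a test of zero ICC; only within-session similarity can. That is correct, and it is the condition used here for the ICC test.

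No conclusion moves: on the SAP's bands, the JPSG and goniometer intervals run from poor to moderate at either n. That stands and is why the point is minor, but it does not make the printed p-values right.

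Finally, the quartiles in Table 3 show spread rather than tails, and they are symmetric for JPSG session 1 (1.33, 2.33, 3.33). So the skewed-data performance figures given with the remedy depend on an assumed lognormal shape.

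**Conclusion.** The concern holds and is minor. The printed p-values treat 64 wrists as independent; this follows from the documents' own figures. That they are too small is conditional on positive left-right correlation: on both the method and the dynamometer for r, and within a session of one method for the ICC. How much too small is unknown because that correlation is not reported. Over an assumed 0.3 to 0.7 the true error rate of a nominal 5% test is about 6% to 11% for Spearman and 5-6% to 9% for the ICC. No verdict at 0.05 changes even at the n = 32 limit.

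Nothing is concluded about the 95% power in the Protocol. No effect size, test or sidedness is given, so whether that calculation also counted wrists as independent cannot be checked.

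**What to change.** Keep all 64 wrists and the present estimates of r and ICC, and state in the SAP that the participant is the sampling unit for every p-value and interval.

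- **P-values:** a permutation test that moves one device's pair of wrists (for the ICC, one session's pair) between participants as a unit. Simulated error at ρ = 0.3, 0.5, 0.7 was 4.7%, 5.1%, 5.6% for r and 4.7%, 4.5%, 4.7% for the ICC.
- **Intervals for r:** a percentile bootstrap resampling participants with both wrists and all devices together; coverage was 94-96%.
- **Intervals for the ICC:** a leave-one-participant-out jackknife on the Fisher z scale with 31 df; coverage was 94-96% with normal data, against 91-94% for the percentile and 91-92% for the BCa participant bootstrap. Print the limits in Table 3.
- **SEM and MDC:** if they are given intervals, the same jackknife on the log scale.
- **Left-right correlation:** report it for each device, within session. This settles the one unknown from data already held.

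A mixed model with participant and wrist-within-participant effects is an alternative that was not tested here.

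The cost is analysis code and SAP wording, with no further participants or measurements. At ρ = 0.3, 0.5, 0.7 intervals widen by about 4-5%, 10-11% and 19-21% for r, and by about 5-6%, 13% and 22-23% for the ICC (normal data). The ICC and SEM intervals remain approximate: under an assumed lognormal shape with log-SD 0.65, close to the session-1 quartiles (goniometer: ln(5.66/2.33)/1.349 = 0.66), the ICC jackknife covered 91-93% and the SEM jackknife 86-90%.

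### Validity is graded by Spearman correlation alone, so the plan gives neither the per-wrist difference from the dynamometer in degrees nor the precision of each grade.

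*SAP*

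**What the plan says.** The Protocol (Instrumentation) says that the Cybex dynamometer "was used as a reference standard to test the validity of the universal goniometer", the inclinometer and the JPSG. Under Procedures, the outcome for every method is an unsigned error in degrees: "The amount of error between the target and achieved angles were recorded as the absolute angular error", and the score is formed "using the arithmetic mean of these three absolute angular errors".

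The SAP (Statistical Analysis) uses Spearman's test for validity and states: "The validity of these three methods was calculated according to their correlation with the isokinetic dynamometer data". It adds: "Correlation coefficients was used to interpret the results". The bands are cut-points of r, for example "between 0.50-0.70 was medium, between 0.30-0.50 was weak, and less than 0.30 was negligible". The Results then call validity "weak for the inclinometer and JPSG and moderately for the goniometer".

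An absolute-agreement measure does appear in the SAP, but only for each method against itself: an ICC ("two-way mixed, absolute agreement) were calculated for test-retest reliability analysis"). Table 2 lists the median and quartiles of each method in degrees beside r. Those figures are unpaired and do not enter the grade. Neither document plans or reports a paired method-minus-dynamometer difference, limits of agreement, or a confidence interval for r.

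**The concern.** When a test method and its reference are scored in the same unit, validity involves two questions. Do they order wrists alike? How far apart are their scores in the same wrist? Spearman's r answers only the first. Adding a constant to every score of one method, or multiplying all of them by a positive constant, leaves the ranks and therefore r unchanged. The validity grade thus cannot register a constant or proportional offset from the dynamometer.

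A grade of weak or moderate validity may be read as a statement about closeness to the reference. It is a statement about ranking. A clinician who wants to know how many degrees a goniometer score may differ from the dynamometer score in one wrist cannot find out from the planned analysis. The grade also rests on a point estimate with no interval, although the bands are only 0.20 wide in the region where the results fall.

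**Working it through.** **Inputs.** SAP Table 2, median (quartiles): dynamometer 3.17° (2.33-4.83); goniometer 3.50° (2.33-4.66), r = 0.529; JPSG 2.50° (1.66-3.33), r = 0.432; inclinometer 3.66° (2.66-5.83), r = 0.350. The sample is 64 wrists from 32 people. The order below is goniometer, JPSG, inclinometer.

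**1. Reproduce Table 2.** t = r·√((n-2)/(1-r²)), two-sided, n-2 degrees of freedom. With n = 64, P = 0.00001, 0.0004 and 0.0046, matching the reported <0.001, <0.001 and 0.005. With n = 32 the values would be 0.002, 0.014 and 0.050, so the reported tests took the wrist as the unit.

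**2. Insensitivity of r.** In a simulated set of 64 pairs, adding 10° to one method moved the mean difference from 0.08° to 10.08°, and tripling its scores moved it to 6.98°. Spearman's r stayed at 0.339 throughout.

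**3. Precision of r.** 95% CI = tanh(atanh(r) ± 1.96/√(n-3)).

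| Method | n = 64 | Bands covered | n = 32 |
|---|---|---|---|
| Goniometer | 0.33-0.69 | weak, medium | 0.22-0.74 |
| JPSG | 0.21-0.61 | negligible, weak, medium | 0.10-0.68 |
| Inclinometer | 0.11-0.55 | negligible, weak, medium | 0.00-0.62 |

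The n = 64 column treats wrists as independent. The n = 32 column is the extreme in which a person's second wrist adds no information; there the goniometer interval covers four bands. With the Bonett-Wright variance for Spearman's r, the n = 64 intervals are 0.310-0.695, 0.197-0.620 and 0.107-0.554, which fall in the same bands.

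**4. What Table 2 gives in degrees.** Median minus 3.17°: +0.33°, -0.67°, +0.49°. These are differences between group medians, not medians of per-wrist differences.

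**5. Illustrative limits of agreement.** Paired data are not given, so this step assumes normal scores, SD = IQR/1.349, mean = average of the three quartiles, and r used as a Pearson correlation.

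- SD: dynamometer 2.50/1.349 = 1.85; goniometer 2.33/1.349 = 1.73; JPSG 1.67/1.349 = 1.24; inclinometer 3.17/1.349 = 2.35.
- Mean: dynamometer 3.44; others 3.50, 2.50, 4.05. Mean gaps: +0.05, -0.95, +0.61.
- SD of difference = √(s₁² + s₂² - 2·r·s₁·s₂) = 1.74, 1.73, 2.43.
- Limits = gap ± 1.96·SD of difference: goniometer -3.4° to +3.5°; JPSG -4.3° to +2.4°; inclinometer -4.2° to +5.4°.

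Centring on the median gaps instead gives -3.1° to +3.7°, -4.1° to +2.7° and -4.3° to +5.2°. Lognormal scores give -4.0° to +4.8°, -5.6° to +2.8° and -4.6° to +7.1°. In most of these cases the wider side exceeds the reference median of 3.17° by a degree or more.

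**6. Would a measure of agreement reorder the methods?** Concordance = 2·r·s₁·s₂/(s₁² + s₂² + gap²) = 0.53, 0.34, 0.33 on the same assumptions. The goniometer is higher and the other two are lower, which is the split the SAP reports.

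**The case against.** The strongest reply is that nothing misleading has been claimed. The SAP does not say that the methods agree with the dynamometer or can replace it, and its grades are already modest. Insensitivity to shift and scale does most harm when r is high. Here the largest r is 0.529 (about 0.55 as a Pearson correlation), and concordance cannot exceed the Pearson correlation. That stands: no agreement analysis could turn these grades into good agreement.

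Second, Table 2 does give medians and quartiles in degrees, so a group-level gap can be read off. That also stands. What is absent is the paired, per-wrist difference.

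Third, limits of agreement would contain more than device error. Each method had its own trials, and the Protocol's Procedures put the dynamometer test in supination and the goniometer, JPSG and inclinometer tests in mid-pronation. On the same crude assumptions, with the Table 3 ICC used as the correlation, each method's seven-day limits against itself are about ±4.7° (goniometer), ±3.3° (JPSG) and ±8.2° (inclinometer). The half-widths against the dynamometer are ±3.4°, ±3.4° and ±4.8°. Much of the difference may therefore be variation in performance. This limits what the paired analysis can be taken to mean. It does not remove the need for one, because the same influences already act on r.

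The choice of a rank method for non-normal data is not in dispute. Percentile or log-scale limits do not need normal scores in degrees either.

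Two stronger readings are tempting. A reader might infer that the ranking of methods is wrong, since the JPSG has a higher r than the inclinometer but a larger median gap. Those gaps are unpaired and carry no interval, and step 6 does not reverse the order. A reader might also put the larger Table 3 inclinometer medians in place of the Table 2 figure and infer a much larger offset. The 3.17° median and r = 0.350 belong to Table 2, no dynamometer median by session is reported, and no method's Table 2 quartiles match either session in Table 3. That combination is not supported.

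**Conclusion.** The point holds as a gap in analysis and reporting. Validity against a reference in the same unit is graded only by a rank correlation, without an interval and without any per-wrist difference in degrees. The intervals for r cover two or three grade bands with 64 independent wrists, and they are wider if a person's two wrists are positively correlated. The illustrative limits are several degrees either side of zero, against a reference median of 3.17°. They rest on assumed distributions and are not estimates from paired data.

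The documents do not show that the weak and moderate grades are wrong, and those grades are unlikely to change. The change should be made because it is cheap and supplies two missing facts: the size of the disagreement and the precision of the grade.

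**What to change.** - Keep Spearman's r. Describe the grade as strength of correlation, not agreement, and give each r a 95% CI from a bootstrap that resamples participants, so that both wrists of a person stay together.
- For each method, report the paired difference from the dynamometer in mean absolute angular error (same wrist, same session, in degrees) with 95% limits of agreement and participant-clustered CIs. Percentile limits stay in degrees; log-scale limits express a ratio and need every score above zero.
- State that these limits include separate performances and different forearm positions, so they are not pure device error, and that the weak and moderate grades are not expected to change.

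The core fix leaves out two items. The documents give no basis for an acceptable difference in degrees, and one set now would be post hoc. Signed errors would need the achieved angles, whereas the Protocol says that absolute errors were recorded.

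**Cost.** A little more analysis of data already collected and a few lines of SAP text. Validity may look less favourable. Precision is moderate: the CI half-width of one limit is 1.96·SD of difference·√(1/n + 1.96²/(2(n-1))), about ±0.7° (goniometer, JPSG) and ±1.0° (inclinometer) with 64 independent wrists, or ±1.0° and ±1.5° at n = 32. These figures assume normal differences; percentile limits would be somewhat less precise.
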